### 9.4.9.1. Adverse Events of Special Interest

Adverse events of special interest will include:

- Adverse eye effects including retina (Section 9.4.7)
- Adverse skin effects including rash (Section 9.4.9.3) and hypopigmentation (Section 9.4.8)
- Peripheral nervous system, central nervous system and muscle effects
- Liver toxicity (Section 9.4.9 and Section 8.1.1)
- Cardiovascular (CV)-type events (including, but not limited to, orthostatic hypotension and QT prolongation) (Section 9.4.9.2)

The topics listed above, as well as new topics which may be subsequently determined by the Sponsor, will be subject to enhanced surveillance activities. Additionally, the topics above will be analyzed for presentation in the Clinical Study Report in accordance with the Statistical Analysis Plan (SAP).

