## 3.3. Benefit/Risk Assessment

To date, no safety issues have been identified that would create an unfavorable benefit-risk balance for LY3314814. The potential benefits are not established but expectation for an effect in slowing AD progression is described above in the Section 3.2. Potential risks include but are not limited to elevated liver enzymes, QT-prolongation with overdose, skin or hair hypopigmentation, rash, retinal changes, and potential interactions with other drugs. The potential risks are monitored with scheduled labs, electrocardiograms (ECGs), skin exams, eye exams, and restrictions on some concomitant medications. More information about the known

and expected benefits, risks, serious adverse events (SAEs) and reasonably anticipated adverse events (AEs) of LY3314814 can be found in the Investigator's Brochure (IB).

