#### 9.4.9.3. Rash

In the event a patient experiences a suspected drug-induced rash, the following procedures should be followed:

- The patient should be referred to a dermatologist for an expert opinion.
- A photograph of the rash should be taken.
- A blood sample should be drawn for PK analysis.
- A punch biopsy may be obtained at the discretion of the dermatologist.

If treatment is discontinued due to a suspected drug-induced rash, the Sponsor-designated medical monitor should be notified as soon as possible, even if the rash did not meet the definition of an SAE.

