6.13.3. Deaths, Other Serious Adverse Events, and Other Notable Adverse Events

Overviews of adverse events will be presented for the Placebo-Controlled period and the Delayed-Start period, respectively, including within each period the number and percentage of subjects who died, experienced serious adverse events, experienced adverse events leading to study discontinuation, and experienced treatment-emergent adverse events. Treatment groups will be compared in the Placebo-Controlled period using Fisher's Exact Test.

Events of the major adverse cardiovascular event type (MACE) that are blindly evaluated by external independent consultants will be summarized and listed.

In addition, the proportion of subjects within specific clusters of TEAEs will be summarized and treatment comparisons will be conducted using Fisher's Exact Test. Clusters will be created from MedDRA High Level Group Terms (HLGTs) and MedDRA SMQ's.

 Table AZET.SAP.2.
 Adverse Events of Special Interest

AE Groups of Interest (Clusters)	MedDRA High Level Group Terms (HLGTs)
Nervous System Disorders	Neuromuscular Disorders HLGT
	Demyelination SMQ
	Peripheral Neuropathy SMQ
Eye Disorders	Retinal disorders SMQ
Skin Disorders	Sub-group A:
	Epidermal and Dermal Conditions HLGT (excluding sub-group B terms)
	Sub-group B (Hypopigmentation-related events):
	Hypopigmentation disorders HLT
	Pigmentation changes, NEC HLT
	Preferred terms: 'hair depigmented', 'eyelash discolouration', 'iris hypopigmentation', 'eye colour change', 'lip colour altered', 'lip discolouration', 'hair colour changes', 'achromotrichia aquired', 'poliosis'
Liver Disorders	Drug related hepatic disorders - comprehensive search SMQ
Cardiovascular-type events – Arrhythmic	Arrhythmia related investigations, signs and symptoms SMQ
	Cardiac arrhythmia terms (incl bradyarrhythmias and tachyarrhythmias) SMQ
	TdP/QT prolongation SMQ
Cardiovascular-type events - Ischemic	Ischaemic heart disease SMQ
Cardiovascular-type events - Stroke	Central nervous system vascular disorders SMQ
Cardiovascular-type events – including orthostatic hypotension	Decreased and Nonspecific Blood Pressure Disorders and Shock HLGT

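### Rash is a named special-interest topic but has no term group of its own: the SAP pools it in a broad skin cluster, so no table counts patients with any rash by arm

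*Protocol*

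**What the plan says.** **Protocol.** Section 3.3 lists potential risks that include "skin or hair hypopigmentation, rash, retinal changes". Section 9.4.9.1 makes skin effects a special-interest topic with two named parts: "Adverse skin effects including rash (Section 9.4.9.3) and hypopigmentation (Section 9.4.8"). It adds that "the topics above will be analyzed for presentation in the Clinical Study Report in accordance with the Statistical Analysis Plan (SAP"). Section 9.4.9.3 sets out a separate work-up: "In the event a patient experiences a suspected drug-induced rash, the following procedures should be followed". The steps are dermatologist referral, a photograph, a blood sample for drug concentration and an optional biopsy.

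**SAP, special-interest clusters.** Under SAP 6.13.3, "the proportion of subjects within specific clusters of TEAEs will be summarized and treatment comparisons will be conducted using Fisher's Exact Test". Table AZET.SAP.2 divides the skin cluster in two. Sub-group A is "Epidermal and Dermal Conditions HLGT (excluding sub-group B terms"). The other is "Sub-group B (Hypopigmentation-related events"). There is no rash group.

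**SAP, other outputs.** Section 6.13.2 tabulates adverse events by preferred term within system organ class, with Fisher's exact test. The tables cover all treatment-emergent events, events by maximum severity, events in at least 2% of subjects, serious events and events that led to stopping treatment. The skin-examination analysis in 6.13.8.2 deals with skin type and hypopigmentation only. No output is described for the rash work-up.

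**The concern.** The protocol treats rash and hypopigmentation as a pair, and the SAP separates out only one of them. Rash then appears in two kinds of table, and neither answers the simple question of how many patients in each arm had any rash.

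- In the cluster table, rash is counted with every other epidermal or dermal event outside sub-group B. Events unrelated to the drug add equally to all arms and dilute a difference.
- In the preferred-term tables, rash is separated from other skin events, but each coded term has its own row. If cases are coded to more than one term, each row carries part of the difference. The rows cannot be added up, because one patient may have several terms.

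What is at stake is the clarity of one safety summary for a risk that the protocol itself names. After the futility stop the reading is largely descriptive, and a count and percentage of patients with any rash is the natural descriptive figure.

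**Working it through.** **1. Denominator.** The documents give no rash rate, no background skin-event rate and no safety power, so the only plan figure to reproduce is the group size (Protocol 10.1, SAP 5.2).

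- Effect size: 2.07/9.78 = 0.212.
- Completers per arm at two-sided 0.025 and 90% power: 2 × (2.241 + 1.282)² / 0.2117² ≈ 554. The t-test version gives 555. The plan states 554.
- Randomized per arm: 554 / (1 − 0.25 × 0.50) = 633.1. The plan states 633, with the placebo arms pooled.

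**2. Test.** Fisher's exact test, as planned for the clusters, at the two-sided 0.05 level of Protocol 10.3.4. Power is obtained by enumerating both binomial counts.

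**3. Dilution in the cluster.** All rates are assumptions. Rash is 2% on placebo and 5% on drug, and the unrelated background *b* is independent of rash and equal in both arms. The cluster rate is 1 − (1 − rash)(1 − *b*).

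| Background *b* | Placebo | Drug | Power |
|---|---|---|---|
| none (rash alone) | 2.00% | 5.00% | 81% |
| 1% | 2.98% | 5.95% | 69% |
| 2% | 3.96% | 6.90% | 60% |
| 3% | 4.94% | 7.85% | 52% |
| 5% | 6.90% | 9.75% | 41% |
| 10% | 11.80% | 14.50% | 27% |
| 15% | 16.70% | 19.25% | 20% |

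The difference shrinks only a little, from 3.00 to 2.55 percentage points. The loss comes mainly from the larger variance at a higher base rate. Other assumed pairs behave in the same way: 2% against 4% has 50% alone and 21%, 14% and 11% at 5%, 10% and 15% background. For 3% against 6% the figures are 70% alone, then 38%, 26% and 19%.

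**4. Fragmentation in the preferred-term tables.** Same 2% against 5%, with one term holding a share of the cases in each arm:

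| Share held by the term | Rates | Power of that row |
|---|---|---|
| 80% | 1.6% v 4.0% | 70% |
| 70% | 1.4% v 3.5% | 63% |
| one half | 1.0% v 2.5% | 46% |
| one third | 0.67% v 1.67% | 29% |
| one quarter | 0.5% v 1.25% | 20% |

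**5. The case that favours the broad cluster.** Suppose the drug also raises related skin terms, from 5% on placebo to 7% on drug. The placebo cluster rate is 1 − 0.98 × 0.95 = 6.90% and the drug rate is 1 − 0.95 × 0.93 = 11.65%. Power is 81%, the same as for rash alone. With a rise from 5% to 8% the drug rate is 1 − 0.95 × 0.92 = 12.60%, and power is 92%.

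**The case against.** **The SAP does not break a protocol commitment.** A reader might infer that the protocol promises a stand-alone rash test. It does not. The topic in 9.4.9.1 is adverse skin effects, of which rash is one named part, and the analysis is left to the SAP. The SAP supplies a skin cluster in two parts, and its revision history shows that this cluster was revised for version 3. Other named topics also sit in wider rows: orthostatic hypotension is in a general blood-pressure group and QT prolongation is in the arrhythmia cluster. This stands.

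**Rash is not hidden.** The tempting stronger reading is that background skin disease could conceal a real excess of rash. The documents do not support it. The all-event table in SAP 6.13.2 has no frequency floor, and severe, serious and treatment-stopping events are shown by term and arm. A reader would see the rash terms. This stands, and it limits the point to dilution and fragmentation.

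**Key premises are not in the documents.** They do not list the terms in the Epidermal and Dermal Conditions group, say how rash will be coded, or give the frequency of other skin events. This also stands. That rash terms fall in sub-group A is itself an assumption; if they do not, rash is in no skin cluster at all.

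**Power is not the decision rule.** SAP 6.1 treats no test as significant, and 633 is the planned number, not the number exposed when the trial stopped. The figures therefore only illustrate dilution. The need for a clean count by arm remains, because low p-values are still to be noted as results of interest and safety is still summarised.

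**Conclusion.** The point holds as a cheap improvement, not as an error in the plan. Rash is a named risk and special-interest topic, its only planned grouping is a broad one, and no table gives the number of patients with any rash by arm.

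The size depends on rates that the documents do not give. For 2% against 5%, dilution is modest if unrelated skin events are rare (81% falls to between 69% and 52% at 1% to 3%) and heavy if they are common (41% to 20% at 5% to 15%). It vanishes if the drug also raises related terms enough (81% at 5% to 7%). The preferred-term rows make up most of the loss only when one term holds most of the cases. These figures assume independence of rash and background, 633 per arm as planned, and rash terms coded within sub-group A. They do not estimate what the actual analysis would miss, and they do not show that the broad cluster is the wrong choice. That last result is the reason to keep sub-group A beside a narrower group.

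**What to change.** In SAP Table AZET.SAP.2:

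- Keep sub-group A as it is.
- Add within it a group of rash and drug-eruption preferred terms. Fix the list before final unblinding, which is also when SAP version 3 is due for approval.
- Show the number and percentage of patients with any term in the group, by arm. For the Placebo-Controlled period, add the Fisher's exact test already planned for clusters. For the Delayed-Start period, give counts only, since SAP 6.13 plans no p-values there.
- State that the comparison is hypothesis-generating, as in SAP 6.1.

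If the database identifies suspected drug-induced rash cases, list them by arm. The documents describe procedures for these cases but no data field that flags them, so this cannot be required. Otherwise, list the rash terms that the investigator judged related, since Protocol 9.2 has relatedness recorded for each adverse event.

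The cost is a term list to agree, a small addition to one table and one listing, all from adverse-event data already collected. The downside is one more unadjusted safety comparison.

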### 9.4.9.2. MACE Adjudication

Alzheimer's disease occurs mainly in elderly people, who may have established CV disease or CV risk factors and constitute a population of patients at increased risk of CV events. Serious CV events, as well as particular arrhythmic events related to QTcF prolongation, are therefore of potential special interest. Serious adverse events that, according to the investigator, may be CV events of the major adverse CV event (MACE) type (myocardial infarction, stroke, or CV death) or may be potential QT prolongation-related arrhythmic events, such as, syncope, ventricular tachycardia/torsades des pointes/fibrillation, or cardiac arrest, will be carefully documented and sent for adjudication. The events will be blindly evaluated by external independent consultants and adjudicated as MACE events per a separate adjudication charter.

#### 9.4.9.3. Rash

In the event a patient experiences a suspected drug-induced rash, the following procedures should be followed:

- The patient should be referred to a dermatologist for an expert opinion.
- A photograph of the rash should be taken.
- A blood sample should be drawn for PK analysis.
- A punch biopsy may be obtained at the discretion of the dermatologist.

If treatment is discontinued due to a suspected drug-induced rash, the Sponsor-designated medical monitor should be notified as soon as possible, even if the rash did not meet the definition of an SAE.

### 9.4.9.4. Vasogenic Edema

If a patient develops symptoms suggestive of vasogenic edema, such as headache, confusion, gait disturbance, or visual disturbance, these should be recorded as AEs and an MRI should be obtained. Study treatment should be discontinued if clinically significant symptomatic vasogenic edema, clinically significant symptomatic superficial siderosis, or clinically significant symptomatic incident microhemorrhage is seen. Following the study treatment discontinuation, the MRI scan should be repeated within 4 weeks to evaluate the status of the finding and then performed every 4 to 6 weeks (or as clinically indicated) until the finding resolves or stabilizes. Treatment with high-dose dexamethasone is to be considered, should symptoms be severe.

#### 9.4.9.5. IDMC

This study will use an IDMC (an independent, external advisory group for this study formed to protect the integrity of data) to monitor data on an ongoing basis to ensure the continuing safety of patients enrolled in the study, to ensure the integrity of the blinded nature of the study, and to oversee any interim analyses (see Section 10.3.7). The IDMC details and structure will be laid out in its charter. In the event that safety monitoring uncovers an issue that needs to be addressed by unblinding at the group level, only members of the IDMC can conduct additional analyses of the safety data.

#### 9.5. Pharmacokinetics

At the visits specified in the Schedule of Activities (Section 2), venous blood samples will be collected to determine the plasma concentrations of LY3314814 and its metabolite AZ13569724. At these visits, the date and time of dosing on the visit day, as well as the date and time of the previous two doses administered will be recorded. Additionally, it will be recorded if the patient consumed a meal within 2 hours before or after dose administration on the day of the study visit. The actual date and time of each sampling will be recorded.

Specific details regarding each of the visits are as follows:

- Visit 4: A phone call will be made 1 day before clinic visit to remind patients to hold the morning dose of study treatment on the day of the visit and bring the dose to the clinic. A blood sample should be collected at arrival, and again at the end of the visit. The patient is to receive the morning dose after the first sample.
- Visit 5: A phone call will be made 2 days before the clinic visit to remind patients to 1) hold the morning dose of study treatment on the day prior to the visit and then take that dose late in the afternoon (at least 14 hours prior to the clinic visit) and 2) hold the morning dose of study treatment on the day of the visit and bring that dose to the clinic. The blood sample may be collected at any time during the visit, and the dose may be administered after the sample is collected.
- Visit 7: A phone call will be made 1 day before clinic visit to remind patients to hold the morning dose of study treatment on the day of the visit and bring the dose to the clinic. A blood sample should be collected at arrival, and again at the end of the visit. Patient is to receive the morning dose after the first sample.
- Visit 10: A phone call will be made 1 day before clinic visit to remind patients to take the morning dose of study treatment as scheduled on the day of the visit, before arriving at the clinic. A blood sample should be collected at the end of the visit
- Visit 11: A phone call will be made 1 day before clinic visit to remind patients to hold the morning dose of study treatment on the day of the visit and bring that dose to the clinic. After cognitive testing is complete, a blood sample should be taken, immediately after which the patient should receive a dose of study treatment. A second blood sample is to be collected 30-45 minutes after dose administration.
- Visit 15: A blood sample will be collected from only those subjects receiving a lumbar puncture. In these patients, a blood sample will be collected at approximately the same time as the lumbar puncture. There are no special instructions for dosing at this visit.

If the patient fails to follow the dosing instructions, blood samples are still to be collected according to the Schedule of Activities (Section 2) and as described above. On those visits where the dose is to be administered at the site, if the patient fails to follow this instruction and is dosed prior to sample collection, an additional dose will not be administered at the visit.

Up to three additional unscheduled PK collections may occur in the event of rash, as part of the assessment of hepatic laboratory abnormalities, or as determined to be warranted by the sponsor.

Drug concentration information that may unblind the study will not be reported to investigative sites or blinded personnel.

Post-baseline CSF samples are to be analyzed for determination of LY3314814 and AZ13569724 concentrations. See Section 9.8.1 for additional details around the collection of CSF samples.

Bioanalytical samples collected to measure investigational product concentration will be retained for a maximum of 1 year following last patient visit for the study. During this time, samples

remaining after the bioanalyses may be used for exploratory analyses such as metabolism and/or protein binding work.

# 9.6. Pharmacodynamics

The peripheral dose-dependent PD activity of LY3314814 and placebo administration will be evaluated by analysis of plasma  $A\beta_{1-40}$  and  $A\beta_{1-42}$  as measured using validated immunoassays. These plasma based biomarkers will provide an assessment of target engagement.

Bioanalytical samples collected to measure plasma  $A\beta_{1-40}$  and  $A\beta_{1-42}$  will be identified by the patient number (coded) and retained for a maximum of 1 year following last patient visit for the study at a facility selected by the Sponsor or its designee.

#### 9.7. Genetics

# 9.7.1. Apolipoprotein E Genotyping

Apolipoprotein E (APOE) genotyping is a mandatory part of this study, unless country-specific laws and regulations prohibit this type of testing. Blood sampling for APOE genotyping will be performed as shown in the in the Schedule of Activities (Section 2). Neither patients nor investigators will receive the genotype results unless there is a country-specific law or regulation that requires notification of the results. Failure to collect samples for APOE will not be considered a protocol violation if country-specific regulations prohibit the testing of genetic material or transportation of such material outside of the country.

# 9.7.2. Whole Blood Samples for Pharmacogenetic Research

A whole blood sample will be collected for pharmacogenetic analysis as specified in the Schedule of Activities (Section 2) where local regulations allow.

Samples will not be used to conduct unspecified disease or population genetic research either now or in the future. Samples will be used to investigate variable response to LY3314814 and to investigate genetic variants thought to play a role in AD and neurodegeneration. Assessment of variable response may include evaluation of AEs or differences in efficacy.

All samples will be coded with the patient number. These samples and any data generated can be linked back to the patient only by the investigator site personnel.

Samples will be retained for a maximum of 15 years after the last patient visit for the study, or for a shorter period if local regulations and/or ethical review boards (ERBs)/investigational review boards (IRBs) impose shorter time limits, at a facility selected by the Sponsor or its designee. This retention period enables use of new technologies, response to regulatory questions, and investigation of variable response that may not be observed until later in the development of LY3314814 or after LY3314814 become(s) commercially available.

Molecular technologies are expected to improve during the 15-year storage period and therefore cannot be specifically named. However, existing approaches include whole genome or exome sequencing, genome wide association studies, and candidate gene studies. Regardless of

technology utilized genotyping data generated will be used only for the specific research scope described in this section.

# 9.8. Biomarkers and Imaging

Biomarker research is performed to address questions of relevance to drug disposition, target engagement, PD, mechanism of action, variability of patient response (including safety), and clinical outcome. Sample collection is incorporated into clinical studies to enable examination of these questions through measurement of biomolecules including deoxyribonucleic acid (DNA), ribonucleic acid (RNA), proteins, lipids, and other cellular elements.

Serum, plasma, CSF, and whole blood RNA samples for non-pharmacogenetic biomarker research and MRI and PET images will be collected at the times specified in the Schedule of Activities (Section 2) where local regulations allow.

Samples and images will be used for research on the drug target, disease process, variable response to LY3314814, pathways associated with AD and neurodegeneration, mechanism of action of LY3314814, and/or research method or in validating diagnostic tools or assay(s) related to AD and neurodegeneration.

All samples and images will be coded with the patient number. These samples and images and any data generated can be linked back to the patient only by the investigator site personnel.

Samples and images will be retained for a maximum 15 years after the last patient visit for the study, or for a shorter period if local regulations and ERBs impose shorter time limits, at a facility selected by the Sponsor or its designee. This retention period enables use of new technologies, response to regulatory questions, and investigation of variable response that may not be observed until later in the development of LY3314814 or after LY3314814 become(s) commercially available.

